13.8 Evaluation of Response

All randomized participants who are evaluated at baseline and 6 months and have IL-1 β cytokine levels from those timepoints will be evaluable for the primary endpoint of this study using the modified intent-to-treat principle. All conclusions regarding efficacy will be based on all participants who completed both baseline and 6 months and have IL-1 β cytokine levels from those timepoints as well. Subanalyses may be performed on the subsets of participants, excluding those for whom major protocol deviations have been identified (e.g., early death due to other reasons, early discontinuation of intervention, major protocol violations, etc.). However, sub-analyses may not serve as the basis for drawing conclusions concerning efficacy, and the reasons for excluding participants from the analysis should be clearly reported. For all measurements of response (i.e. the primary endpoint), the 95% confidence intervals will also be provided.

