13.2 Randomization/Stratification

Participants will be randomized in a 1:1 fashion to one of two arms (Meriva® vs. placebo), using a dynamic allocation procedure called the Pocock-Simon, which balances the marginal distributions of the stratifications factors across the intervention groups and has been shown to be able to accommodate a large number of factors (10-20) without difficulty. For this study we will use the following stratification factors (collected at baseline, prior to randomization): enrolling site (Honduras or Puerto Rico) and gastric mucosal histologic diagnosis (MAG, GIM, or both).

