13.4 Primary Objective, Endpoint(s), Analysis Plan

The primary endpoint of this randomized trial is to compare the absolute change in IL-1 β cytokine levels (measured by Luminex assay) in the gastric mucosa from baseline to 6 months among participants randomly assigned to receive either Meriva® or placebo. Statistical considerations regarding sample size and study power are based on this primary study endpoint.

In total, approximately 100 individuals will be screened and 50 participants will be randomized to receive Meriva® (n=25) or placebo (n=25), in order to achieve complete trial data on 22 evaluable participants in each arm (44 evaluable total). This assumes a 10% over accrual buffer after randomization to account for participants who are deemed ineligible, cancel, or dropout for other reasons during the intervention period. We expect to randomize approximately 5-6 participants per month across both the Puerto Rico and Honduras recruiting sites.

The null hypothesis for this study is that the absolute change in the IL-1 β values from baseline to 6 months is the same or increased for Meriva® vs. placebo. The alternative hypothesis is that Meriva® intervention will lead to a significant decrease in IL-1 β cytokine levels from baseline to 6 months, as compared to placebo. The proposed sample size and power calculations are based on prior unpublished data, where IL-1 β levels are expected to have a mean of approximately 14 pg/mg protein at baseline, with a standard deviation of about 7.5 pg/mg of protein. This prior mouse study showed a 2-fold decrease in IL-1 β levels for curcumin-treated mice (from around 14 to 7 pg/mg protein, comparing the vehicle [equivalent to placebo] treated to curcumin-treated mice). Based on this prior data, we expect the Meriva®-treated participants to have a mean decrease of about 7 pg/mg of protein or more by 6 months after baseline, leading to a 6 month IL-1 β mean of 7 pg/mg of protein in the Meriva®-treated participants (2-fold decrease). For the placebo group, we expect the mean IL-1 β to either stay the same or decrease slightly from baseline to 6 months.

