With 22 evaluable participants per arm, this study yields 88% power to detect a mean decrease of 7 pg/mg protein or more in IL-1 β level in the Meriva® intervention arm compared to a mean decrease of 0.5 pg/mg protein in the placebo arm (from baseline to 6 months), with an overall 1-sided significance level of 0.05 (2 sample t-test, assuming the same standard deviation of 7.5 pg/mg protein in each arm). If the data are not normally distributed, we will use the Wilcoxon Rank-Sum test for the primary endpoint analysis.

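### Does a 95% confidence interval beside a one-sided 0.05 primary test leave the trial's conclusion unclear?

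*Combined protocol and SAP*

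**What the plan says.** Section 13.4 sets a directional null hypothesis: for Meriva against placebo, the absolute change in IL-1β "values from baseline to 6 months is the same or increased". The alternative is a greater decrease on Meriva. The power statement in the same section reads "With 22 evaluable participants per arm, this study yields 88% power to detect a mean decrease of 7 pg/mg protein or more" on Meriva, "compared to a mean decrease of 0.5 pg/mg protein in the placebo arm", "with an overall 1-sided significance level of 0.05". The method is given as "2 sample t-test, assuming the same standard deviation of 7.5 pg/mg protein in each arm". A fallback follows: "If the data are not normally distributed, we will use the Wilcoxon Rank-Sum test for the primary endpoint analysis". Section 13.2 fixes equal allocation: "Participants will be randomized in a 1:1 fashion to one of two arms".

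Section 13.8 defines who is evaluable for the primary endpoint, bases efficacy conclusions on that set, and ends with the sentence at issue: "For all measurements of response (i.e. the primary endpoint), the 95% confidence intervals will also be provided". It does not say whether the interval is one-sided or two-sided, or whether it is for the between-arm difference or for the change within each arm. Neither section names a 90% interval or an interval to accompany the Wilcoxon test.

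**The concern.** A two-sided 95% interval for a difference in means excludes zero on the benefit side only when the one-sided p-value is below 0.025. The test in section 13.4 rejects below 0.05. The interval that matches that test is the two-sided 90% interval or a one-sided 95% bound. Read in the usual way, the plan therefore pairs its primary test with an interval calibrated to a stricter level. A result with one-sided p between 0.025 and 0.05 would be declared positive and published beside an interval that contains no effect.

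If the plan gave no way to choose between the two statements, the emphasis could be settled after unblinding, and readers might doubt whether the primary objective was met. That would matter in a small trial with one primary biomarker.

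**Working it through.** **Inputs.** All are from section 13.4: 22 evaluable per arm, SD 7.5 pg/mg in each arm, a fall of 7 on Meriva and 0.5 on placebo, two-sample t-test, one-sided 0.05. The design difference is 7 − 0.5 = 6.5 pg/mg. Differences below are the extra fall on Meriva.

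**Step 1: reproduce the plan's power.**
- Standard error = 7.5 × √(2/22) = 2.261 pg/mg, with 22 + 22 − 2 = 42 degrees of freedom.
- Noncentrality = 6.5 / 2.261 = 2.874.
- One-sided 0.05, critical t = 1.682: noncentral-t power is 88.2%, which agrees with the stated 88%.
- One-sided 0.025 (the benefit side of a two-sided 0.05 test), critical t = 2.018: power is 80.2%, which does not agree.

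The design level is therefore one-sided 0.05, as written. The word one-sided is not a slip.

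**Step 2: where test and interval part.** The smallest observed difference meeting each criterion is the critical t times the standard error:
- the test rejects from 1.682 × 2.261 = 3.80 pg/mg;
- a two-sided 95% interval excludes zero from 2.018 × 2.261 = 4.56 pg/mg.

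The window is 4.56 − 3.80 = 0.76 pg/mg wide at the planning SD.

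**Step 3: an example inside the window.** For an observed difference of 4.0, t = 4.0 / 2.261 = 1.769 and the one-sided p is 0.042. The 95% interval is 4.0 ± 4.56, or −0.56 to 8.56. The 90% interval is 4.0 ± 3.80, or 0.20 to 7.80.

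**Step 4: how often.** The probability of landing in the window is the rejection probability at one-sided 0.05 minus that at one-sided 0.025.

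| True difference (pg/mg) | Test positive | 95% interval excludes 0, benefit side | In the window | Share of positives |
|---|---|---|---|---|
| 0 | 5.0% | 2.5% | 2.5% | 50% |
| 4 | 53.8% | 40.8% | 13.0% | 24% |
| 6.5 | 88.2% | 80.2% | 8.0% | 9% |

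These figures are for the t-test and do not cover the Wilcoxon fallback.

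**Step 5: what a change would do.** Replacing the 95% interval by a two-sided 90% interval makes interval and test agree exactly. The 22 per arm, the 88.2% power and every accept-or-reject outcome stay as they are. Lowering the test to one-sided 0.025 would also align them, but power would fall to 80.2%, and about 28 evaluable per arm would be needed to keep 88%.

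**Step 6: what governs.** Section 13.4 supplies the hypothesis, the test and its level. Section 13.8 ties efficacy conclusions to an analysis set and adds the intervals as further reporting. Neither section makes a conclusion depend on an interval excluding zero.

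**The case for a change.** The best case for a change is that the remedy is a single sentence and the situation is not remote. The design effect is borrowed from a mouse experiment, so a smaller effect in people is plausible. At a true difference of 4 pg/mg, about a quarter of positive results would come with a 95% interval that includes zero. Section 13.8 does not call the interval descriptive, and it sits in the section that says what efficacy conclusions rest on. If the Wilcoxon test is used, the plan names no estimate or interval to go with it.

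The frequencies stand, as does the observation that the interval is under-specified. The inference to a defect does not. A one-sided p of 0.042 and a two-sided 95% interval of −0.56 to 8.56 are both correct statements from the same data at different error levels, and a reader who sees both can reconcile them. Whether the objective was met is answered by the test fixed in advance. The 2.5% under no effect is part of the 5% error rate that the design openly accepts, not an addition to it. The mismatch also needs two readings that the text does not state: that the interval is two-sided and that it is for the between-arm difference. The first is the usual meaning. The second is open, and for within-arm intervals the correspondence with the test does not arise. For the fallback, a Hodges-Lehmann shift with its interval is a natural companion that an analyst can add without an amendment.

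**Conclusion.** No change to the plan is called for. The one-sided 0.05 test is the single decision rule, and its power reproduces at 88.2%. The 95% interval is a valid supplementary estimate. If it is two-sided and for the between-arm difference, observed differences from 3.80 to 4.56 pg/mg would be significant with an interval that includes zero. That assumes SD 7.5, 22 per arm and the t-test. The probability depends on the unknown true difference: about 8% at 6.5, 13% at 4 and 2.5% at zero.

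Headlining a 90% interval is a presentational preference on which statisticians differ. The more familiar 95% level gives readers a stricter view of precision, and the cost is an occasional result that looks awkward. Sidedness, the quantity estimated and the interval for the fallback are details that can be stated when results are reported, together with a note that the one-sided test decides. None of them alters the sample size, the test, the analysis set or the trial's conclusion.

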13.9 Interim Analysis

Not applicable

13.10 Ancillary Studies

Not applicable

14. ETHICAL AND REGULATORY CONSIDERATIONS

14.1 Form FDA 1572

Prior to initiating this study, the Protocol Lead Investigator at the Lead or Participating Organization(s) will provide a signed Form FDA 1572 stating that the study will be conducted in compliance with regulations for clinical investigations and listing the investigators, at each site that will participate in the protocol. All personnel directly involved in the performance of procedures required by the protocol and the collection of data should be listed on Form FDA 1572.

14.2 Other Required Documents

- 14.2.1 Current (within two years) CV or biosketch for all study personnel listed on the Form FDA 1572 and Delegation of Tasks form for the Lead Organization and all Participating Organizations.
- 14.2.2 Current medical licenses (where applicable) for all study personnel listed on Form FDA 1572 and Delegation of Tasks form for the Lead Organization and all Participating Organizations.
- 14.2.3 Lab certification (*e.g.*, CLIA, CAP) and lab normal ranges for all labs listed on Form FDA 1572 for the Lead Organization and all Participating Organizations.
- 14.2.4 Documentation of training in "Good Clinical Practice" for all study personnel listed on the FDA Form 1572 and on the Delegation of Tasks forms for the Lead Organization and all Participating Organizations.
- 14.2.5 Documentation of Federalwide Assurance (FWA) number for the Lead Organization and all Participating Organizations.
- 14.2.6 Signed Investigator's Brochure/Package Insert acknowledgement form
- 14.2.7 Delegation of Tasks form for the Lead Organization and all Participating Organizations signed by the Principal Investigator for each site and initialed by all study personnel listed on the form
- 14.2.8 Signed and dated NCI, DCP Financial Disclosure Form for all study personnel listed on Form FDA 1572 for the Lead Organization and all Participating Organizations

14.3 Central Institution Review Board (CIRB) and Review of Ethics Board Approval

Prior to initiating the study and receiving agent, the Investigators at the Lead Organization and the University of Puerto Rico must obtain written approval to conduct the study from the appropriate CIRB. The Honduras site must obtain written approval to conduct the study from the appropriate Review of Ethics Board. Should changes to the study become necessary, protocol amendments will be submitted to the DCP PIO according to DCP Amendment Guidelines. The DCP-approved amended protocol must be approved by the CIRB/REB prior to implementation

14.4 Informed Consent

All potential study participants will be given a copy of the IRB-approved Informed Consent to review. The investigator will explain all aspects of the study in lay language and answer all questions regarding the study. If the participant decides to participate in the study, he/she will be asked to sign and date the Informed Consent document. The study agent(s) will not be released to a participant who has not signed the Informed Consent document. Subjects who refuse to participate or who withdraw from the study will be treated without prejudice.

Participants must be provided the option to allow the use of blood samples and tissues obtained during testing, operative procedures, or other standard medical practices for further research purposes. If applicable, statement of this option may be included within the informed consent document or may be provided as an addendum to the consent.

Prior to study initiation, the informed consent document must be reviewed and approved by NCI, DCP, the Consortium Lead Organization, and the CIRB/REB, as applicable at each Organization at which the protocol will be implemented. Any subsequent changes to the informed consent must be approved by NCI, DCP, the Consortium Lead Organization's IRB, and then submitted to each organization's IRB for approval prior to initiation.

14.5 Submission of Regulatory Documents

All regulatory documents are collected by the Consortia Lead Organization and reviewed for completeness and accuracy. Once the Consortia Lead Organization has received complete and accurate documents from a participating organization, the Consortium Lead Organization will forward the regulatory documents to DCP's Regulatory Contractor:

Paper Document/CD-ROM Submissions:

Regulatory Affairs Department CCS Associates, Inc. [name]

[contact]; [contact]

E-mail submissions: [contact]

Regulatory documents that do not require an original signature may be sent electronically to the Consortium Lead Organization for review, which will then be forwarded electronically to DCP's Regulatory Contractor.

14.6 Other

This trial will be conducted in compliance with the protocol, Good Clinical Practice (GCP), and the applicable regulatory requirements.

APPENDIX A

Performance Status Criteria

Grade	ECOG Performance Status Scale Descriptions
0	Normal activity. Fully active, able to carry on all pre-disease performance without restriction.
1	Symptoms, but ambulatory. Restricted in physically strenuous activity, but ambulatory and able to carry out work of a light or sedentary nature (e.g., light housework, office work).
2	In bed <50% of the time. Ambulatory and capable of all self-care, but unable to carry out any work activities. Up and about more than 50% of waking hours.
3	In bed >50% of the time. Capable of only limited self-care, confined to bed or chair more than 50% of waking hours.
4	100% bedridden. Completely disabled. Cannot carry on any self-care. Totally confined to bed or chair.
5	Dead.

APPENDIX B

Medication and Symptom Diary

Participant ID:		Physician:	M	onth	Year	_
		or you to record how		B 8		
And the second s		the day you notice t		The state of the s		5 COLOR DO C
	A STATE OF THE PARTY OF THE PAR	ottles with any unuse	NAME OF TAXA	60 NO		PR 52
15		at about the same tir	mes each day. If you	miss a dose, leave th	ie check box blank to	r that dose. If you
nave any questions,	, please contact:					
Sunday	Monday	Tuesday	Wednesday	Thursday	Friday	Saturday
						
am pm	∐ am ∏ pm	am pm	∐ am □ nm	am pm		am D nm
 	 	 		 	 	□ pm
□am	□am	□am	□am	□am	□am	□ am
pm	☐ pm	pm	pm	pm pm	pm	pm
am	am	am	am	am	am	am
pm	pm	pm	pm	pm	pm	pm
am	am	am	am	am	am	am
 pm	 pm	 pm	 pm	 pm	☐ pm	pm
		_			l 	
am	am	am	am	am	am	am
l I nm	l l nm	l l nm	I I I nm	l l nm	I I I nm	nm

[figure not shown]
MAY2015-05-01 Version 4.0, Amendment 6 May 13, 2019

		May 13, 2019
	to report, please make note of them on this page. Be sure to write down is. If you took any medications for the symptom or visited a doctor or hos	
Participant signature	, Date	
- di cioipante signature	, Duice	
Study Coordinator signature	, Date	

Appendix C. Was It Worth It (WIWI) Questionnaire

Visit type (Time point):* Me	onth 6 (or early termination)			
	/ research study is a personal choice and get your feedback on your experience ing questions as indicated.			study.
Directions : Please answer eac	h question by circling Y (for yes), N (for n	o), or U (f	or un	certain).
Was it worthwhile for you to p	participate in this research study?	Υ	N	U
If you had to do it over, would	you participate in this research study aga	ain? Y	N	U
Would you recommend partici	pating in this research study to others?	Υ	N	U
Directions : Circle one respons	se			
Overall, did your quality of life	change by participating in this research	study?		
It improved	It stayed the same It got worse			
Overall, how was your experie	nce of participating in this research study	/ ?		
Better than I expected	The same as I expected Wor	se than I e	xpect	:ed
If there was one thing that coustudy, what would it be?	uld have been done to improve your exp	perience ir	n this	research
Would you like to talk to some	eone about your concerns (circle one re	sponse)?	Yes	No
Signature	 Date			

Appendix D. Gastric Biopsy Map

Appendix E. Alcohol Assessment: Baseline

Instructions: For the following questions about drinking alcoholic beverages, a drink means a 12 oz. beer, a 5 oz. glass of or one and a half ounces of liquor. 1. In your entire life, have you had at least 12 drinks of any kind of alcoholic beverage? (check one) Yes ☐ No (End) Choose not to answer (End) Don't know/Not sure (If No or Choose not to answer), stop assessment 2. In the past 12 months, on average, how often did you drink any type of alcoholic beverage? (Enter the number of days drank based on the timeframe checked below. Enter 0 if you never drank and skip to Question 6.) (If more than 0, check one) ☐ Week Month Year Choose not to answer Don't know/Not sure 3. In the past 12 months, on those days that you drank alcoholic beverages, on average, how many drinks did you have (Enter the average number of drinks per day) (If no answer, check one) Choose not to answer Don't know/Not sure In the past 12 months, on how many days did you have 5 or more drinks of any alcoholic beverage? (Enter the number of days you had 5 or more drinks, or enter 0 if none.) (If no answer, check one) Choose not to answer Don't know/Not sure 5. Was there ever a time or times in your life when you drank 5 or more drinks of any kind of alcoholic beverage almost (day? (check one) Yes No Choose not to answer Don't know/Not sure 6. If you do not currently drink alcoholic beverages, but did in the past, how long has it been since you last drank regularl (check one) Within the past month (0 to 1 month ago) Between 1 and 3 months (1 to 3 months ago) Between 3 and 6 months (3 to 6 months ago) Between 6 and 12 months (6 to 12 months ago) Between 1 and 5 years (1 to 5 years ago) Between 5 and 15 years (5 to 15 years ago) ☐ More than 15 years ago Don't know/Not sure Never drank regularly

Choose not to answer

Alcohol Assessment: Baseline (continued)

7.	At the heaviest point, either now on the average? (Enter the number	or in the past, on the days when you drank, about how many drinks did you drink a day or of drinks a day)
	(If no answer, check one)	· ,,
	Choose not to answer	
	☐ Don't know/Not sure	
8.	How many years have you been dr (If no answer, check one)	inking (or did drink) regularly? years
	☐ Choose not to answer	
	☐ Don't know/Not sure	
9.	At what age did you begin drinking (If no answer, check one) Choose not to answer Don't know/Not sure	regularly? years of age
10.	What type(s) of alcohol do you dri	nk?
	Wine	(check one) Yes No Choose not to answer
	Liquor	(check one) Yes No Choose not to answer
	Beer	(check one) Yes No Choose not to answer
	Wine cooler	(check one) Yes No Choose not to answer

Appendix E. Alcohol Assessment: Follow-Up

Instructions: For the following questions about drinking alcoholic beverages, a drink means a 12 oz. beer, a 5 oz. glass of wine, or one and a half ounces of liquor.

During the past 30 days, did you drink any alcoholic beverages? (check one)
Yes
□ No (End)
Choose not to answer (End)
☐ Don't know/Not sure
(If No or Choose not to answer, stop assessment)
During the past 30 days, how many days per week or per month did you drink any alcoholic beverages, on the average (Enter number of days you drank based on the timeframe checked below. Enter 0 if you did not drink.) (If more than 0), specify (check one)
☐ Week
Month
Choose not to answer
☐ Don't know/Not sure
On the days when you drank, on average, about how many drinks did you have?
(Enter the average number of drinks you had per day.)
(If no answer, check one)
☐ Choose not to answer ☐ Don't know/Not sure
Don't know/Not sure
In the past 30 days, on how many days did you have 5 or more drinks per day?(Enter the number of days you had 5 or more drinks, or enter "0" if none)
(If no answer, check one)
None
☐ Choose not to answer
□ Do not know/Not sure

Appendix E. Tobacco Assessment: Baseline

Section A. Basic Cigarette Use Information 1. Have you smoked at least 100 cigarettes (5 packs = 100 cigarettes) in your entire life?
 Yes
☐ Choose not to answer → Skip to Section B
\square No \rightarrow Skip to Section B
☐ Don't know/Not sure → Skip to Section B
2. How old were you when you first smoked a cigarette (even one or two puffs)? Years old (If no answer, check one) Choose not to answer Don't know/Not sure
3. How old were you when you first began smoking cigarettes regularly? Years old (If no answer, check one) Refused Don't know/Not sure Check here if you have never smoked cigarettes regularly.
4. How many total years have you smoked (or did you smoke) cigarettes? Do not count any time you may have stayed off cigarettes. (If you smoked less than one year, write "1.")Years
Choose not to answer Don't know/Not sure
5. On average when you have smoked, about how many cigarettes do you (or did you) smoke a day? (A pack usually has 20 cigarettes in it) Number of cigarettes per day (If no answer, check one) Choose not to answer Don't know/Not sure
6. Do you NOW smoke cigarettes? (check one) Everyday Some days
☐ Choose not to answer → Skip to question 8
Not at all → Skip to question 8
7. How soon after you wake up do you smoke your first cigarette? (check one) Within 30 minutes
8. How long has it been since you last smoked a cigarette (even one or two puffs)? First check which one of the following choices applies to you. Then, if applicable, write a number on the line for how many days, weeks, months, or years it has been since your last cigarette.
I smoked a cigarette today (at least one puff) (check one) Yes No
1-7 days (check one) Yes No
(If yes), Number of days since last cigarette
Less than 1 month (check one) Yes No
(If yes), Number of weeks since last cigarette
Less than 1 year (check one) Yes No
(If yes), Number of months since last cigarette
More than 1 year (check one) Yes No
(If yes), Number of years since last cigarette
Don't know/Don't remember (check one) Yes No
Choose not to answer

Tobacco Assessment: Baseline (continued)

Section B. Use of Other Forms of Tobacco

 9. Have you ever used other forms of tobacco, not including cigare ☐ Yes ☐ Choose not to answer ☐ No → Skip to Section C 	ettes? (check one)
Some days (check one) Yes No (If yes) , Number of (If yes) , Per (	(select one) Week Month Year
11. Which of the following products have you ever used regularly?	(Mark yes, no., or choose not to answer for all choices)
Cigarettes	(check one) Yes No Choose not to answer
Traditional cigars, cigarillos or filtered cigars	(check one) Yes No Choose not to answer
Hookah	(check one) Yes No Choose not to answer
Bidis	(check one) Yes No Choose not to answer
Snus	(check one) Yes No Choose not to answer
E-cigarettes or other electronic nicotine delivery system	(check one) Yes No Choose not to answer
Pipes	(check one) Yes No Choose not to answer
Water pipe	(check one) Yes No Choose not to answer
Clove cigarettes or kreteks	(check one) Yes No Choose not to answer
Smokeless tobacco (like dip, chew, or snuff)	(check one) Yes No Choose not to answer (check one) Yes No Choose not to answer
Paan with tobacco, gutka, zarda, khaini Other, Otherspecify:	(check one) Yes No Choose not to answer
 □ Between 1 and 3 months (1 to 3 months ago) □ Between 3 and 6 months (3 to 6 months ago) □ Months (6 to 12 months ago) □ Donths (6 to 12 months ago) 	ween 1 and 5 years (1 to 5 years ago) ween 5 and 15 years (5 to 15 years ago) re than 15 years ago o't know/Not sure rose not to answer
 14. In the past 30 days, have you lived in a place where other peop Yes No Choose not to answer 15. In the past 30 days, have you worked in a place where other peop Yes No Choose not to answer 	
16. Thinking of all your childhood and adult years, have you ever livindoors? (check one) ☐ Yes → In total, for about how many years? If less ☐ No ☐ Choose not to answer	
17. Thinking of all the years you have worked, have you ever worked (check one) ☐ Yes → In total, for about how many years? If less ☐ No ☐ Choose not to answer	

